## 12.0 INVESTIGATIONAL MEDICINAL PRODUCT

### 12.1 Investigational Medicinal Product Supplies and Packaging

Safinamide will be manufactured according to current Good Manufacturing Practice (GMP) compliance standards and supplied as film-coated tablets containing 50 mg or 100 mg of active substance for oral administration. A description of safinamide is given in Table 3.

**TABLE 3 DESCRIPTION OF INVESTIGATIONAL MEDICINAL PRODUCT (SAFINAMIDE)**

| Characteristic  | Investigational Product                                |
|---|--|
| Product name  | Safinamide   |
| Active ingredient   | Safinamide methanesulfonate                            |
| Physical appearance   | Orange to copper, round, biconcave film-coated tablets |
| Dosage  | Once daily   |
| Unit dose strength  | 50 mg, 100 mg safinamide (free base)                   |
| Route of administration                                       | Oral   |
| Treatment duration  | 16 weeks   |
| Manufacturer                                      | Zambon S.p.A. Vicenza                                  |
| Company performing primary packaging                          | Zambon S.p.A. Vicenza                                  |
| Company performing secondary packaging/labelling  | Parexel  |

 Manufactured according to current Good Manufacturing Practice.

 Labelling will conform to applicable regulatory requirements.

Each tablet consists of safinamide methanesulfonate combined with the following inactive ingredients: microcrystalline cellulose, crospovidone, colloidal silicone dioxide, magnesium stearate, and for the coating: purified water, hypromellose and polyethylene glycol. Candurin® pigments are included for colour modification.

Safinamide film-coated tablets, 50 and 100 mg, will be supplied in PVC/PVDC60/AI blisters.

A sufficient quantity of safinamide film-coated tablets (50 mg and 100 mg) will be supplied by the Sponsor, together with certificates of analysis, material safety data sheets, expiry dates and a statement that the study medication has been manufactured in accordance with GMP.

Placebo film-coated tablets are composed of the inactive ingredients used in the safinamide tablets (microcrystalline cellulose, crospovidone, colloidal silicone dioxide, magnesium stearate, and for the coating: purified water, hypromellose and polyethylene glycol). Candurin® pigments are included for colour modification. A description of placebo is given in [Table 4](#).

Placebo film-coated tablets, 50 and 100 mg, will be supplied in PVC/PVDC60/AI blisters.

A sufficient quantity of placebo film-coated tablets (50 mg and 100 mg) will be supplied by the Sponsor, together with certificates of analysis, material safety data sheets, expiry dates and a statement that the study medication has been manufactured in accordance with GMP.

**TABLE 4 DESCRIPTION OF INVESTIGATIONAL MEDICINAL PRODUCT (PLACEBO)**

| Characteristic  | Investigational Product                                |
|---|--|
| Product name  | Placebo  |
| Physical appearance   | Orange to copper, round, biconcave film-coated tablets |
| Dosage  | Once daily   |
| Unit dose strength  | 50 mg, 100 mg  |
| Route of administration                                       | Oral   |
| Treatment duration  | 16 weeks   |
| Manufacturer                                      | Zambon S.p.A. Vicenza                                  |
| Company performing primary packaging                          | Zambon S.p.A. Vicenza                                  |
| Company performing secondary packaging/labelling  | Parexel  |

 Manufactured according to current Good Manufacturing Practice.

 Labelling will conform to applicable regulatory requirements.

Study medication will be labelled in accordance with GMP and country-specific regulations as required by the regulatory bodies in the country where the study is conducted. Labels will be printed in the local language.

As part of the drug packaging and distribution process, emergency unblinding envelopes will be produced and distributed to the Sponsor's pharmacovigilance unit. These sealed individual patient unblinding envelopes will bear the medication kit number on the outside and also include the relevant unblinded study treatment on the inside of the security envelope.

## **12.2 Investigational Medicinal Product Dispensing and Administration**

The first dose of safinamide or placebo (50 mg) will be administered at the study centre following completion of all baseline assessments and based on randomization list. Patients will take subsequently 50 mg od safinamide (or placebo) at home (i.e. either unsupervised or with the assistance of a caregiver) in the morning (at breakfast time, in addition to the morning dose of L-dopa and other, if any, PD medications) for 2 weeks and increase then the dose to 100 mg/day the day after the Visit 3/week 2, ideally at day 15 (at home).

Treatment with oral safinamide (or placebo) 100 mg od will continue up to week 16 and will be self-administered (i.e. either unsupervised at home or with the assistance of a caregiver) at approximately the same time each day. On study visits after visit 2, patients should take their dose of safinamide/placebo in the morning prior to attending the study centre.

Patients will be asked to return all unused medication to the study centre for compliance calculation ([Section 10.2](#)).

*Throughout the study, patients will continue to take their standard, prescribed anti-Parkinsonian treatment; doses must be kept constant.*

*In the case of intolerable dopaminergic adverse events (AEs), e.g. dyskinesia, it is suggested to decrease the dose of L-dopa by a telephone call as a first step and consider the decrease of the dose of safinamide or placebo from 100 to 50 mg od as a second step. In this second case, patients should undergo an unscheduled visit for safety reasons and maintain the 50 mg dose for the rest of the study. Patients who do not tolerate the 50 mg*

dose should withdraw from the study and complete the early termination visit assessments, when possible.

The patients will be provided at each visit with sufficient IMP for the treatment until the following visit, including additional spare tablets.

Study medication will be stored on-site in accordance with the label requirements in a secure area with access limited to the Investigator and authorised study personnel.

No special procedures for the storage or the safe handling of the study medication are required. The Sponsor and their authorised representatives such as study monitors or auditors as well as regulatory inspectors will be permitted, upon request, to audit the supplies, storage and dispensing procedures and records in accordance with applicable regulatory requirements.

Once medication has been dispensed to study patients, it should be stored in accordance with the instructions on the label.

### **12.3 Randomisation**

Patients who meet all criteria for enrolment will be randomised to double-blind treatment in a 1:1 ratio either to safinamide or placebo at visit 2 (day 1) and will be allocated a medication kit number according to the randomised treatment group. The randomisation will be done with blocks sized of unequal length to guarantee a good balance between safinamide and placebo at any stage of the enrolment minimizing the procedure selection bias.

#### **Patient identification:**

Each patient who has signed an informed consent form and is screened will be allocated to a 3-digit screening number comprising the prefix 'xx' where xx is the unique site number and a 3-digit number representing the sequential order in which they are screened, e.g. 01-001, 01-002, 02-001 etc.

The number will be assigned by the eCRF/IWRS upon entry in the system.

#### **Kit number**

At randomisation, the eCRF/IWRS will allocate a unique medication kit number.

### **12.4 Investigational Medicinal Product Accountability**

IMP inventory and accountability records will be kept by the Investigator or Pharmacy. The following rules are to be followed:

- a) the Investigator will keep IMP in a pharmacy, or a locked and secure storage facility, accessible only to those individuals authorised by the Investigator to dispense the IMP.
- b) the inventory will be maintained by the Investigator or pharmacist or other nominated individual. The inventory will be done by means of a specific "Subject/Study Investigational Product Accountability Record & Investigational Product Reconciliation Log" provided by the CRO/IWRS and will include details of IMP received and a clear record of when they were dispensed and to which patient. The log shall indicate the quantity and description of all IMPs on hand at any time during the course of the clinical trial.
- c) at the conclusion or termination of the clinical trial, the Investigator agrees to conduct a final IMP inventory and to record the results of the inventory on an appropriate form

provided by the CRO/IWRS (Investigational Product Return Form). The monitor will check that IMP accountability was correctly performed. According to instructions, the Investigator will return all original IMP containers, whether empty or containing test preparations, to local depot delegated by the CRO for final reconciliation and destruction. Sites can also handle destruction.

- d) the IMP can be dispensed to patients only by Investigator/pharmacist who agrees not to supply IMP to any person except those named as Investigators/Co-Investigators as detailed in the Site Signature/Delegation Log, and to patients in this trial.

## 12.5 Treatment of Overdose

Reports of overdose with safinamide have been rare. The anticipated pattern of events or symptoms following intentional or accidental overdose with safinamide is that related to its pharmacodynamic profile (MAO-B inhibition with activity-dependent inhibition of sodium channels). The symptoms of excessive MAO-B inhibition (increase in dopamine level) could include hypertension, postural hypotension, hallucinations, agitation, nausea, vomiting and dyskinesia.

There is no known antidote to safinamide or any specific treatment for a safinamide overdose. If a significant overdose should occur, safinamide treatment should be discontinued and supportive treatment should be administered as clinically indicated.

## 13.0 CLINICAL TRIAL AMENDMENTS

Changes to the Clinical Trial Protocol (CTP) can be made by preparing written amendments to be agreed and signed by the Investigator and Sponsor. A substantial amendment may not be implemented without a favourable opinion of the Ethics Committee (EC) and Competent Authority (CA), unless the changes consist of urgent safety measures to protect trial patients.

Amendments which are non-substantial amendments as defined by present regulations can be sent to EC/CA for notification and may be implemented at the site before EC/CA notification according to local rules.

## 14.0 DEVIATIONS FROM THE CLINICAL TRIAL PROTOCOL

Any major or critical deviation which may have an impact on study results and safety of the patients should be immediately reported to Sponsor/CRO and notified to Regulatory Authorities (EC/CA) according to local regulations. A decision will be taken together with the Sponsor whether or not the patient affected by the deviation from the CTP is to continue in the study. The deviation from the CTP can be referred to relevant data points recorded on eCRF. A deviation log will be maintained to track actual deviations and decisions taken, including all deviations occurred.

In case of an emergency deviation from the CTP applicable only when an emergency situation has to be faced for a patient, this deviation will be only applied to that individual.

In such an emergency the Investigator must contact the CRO by telephone as soon as possible.

## 14.1 Code Breaking

The code for any individual patient will not be broken by the Investigator during course of the trial except in the circumstance of an SAE of life-threatening significance.

In case of emergency, unblinding of the treatment code will be done through IWRS. The treatment group will be disclosed and confirmation will follow (by fax and/or notification email). The IWRS will be designed to send a confirmation (by fax and/or notification email) to the site for every transaction performed by the site users. Site users will be provided with usernames and passwords to access the IWRS.

Unblinding of the study treatment must be done in case of an emergency situation, where the Investigator considers it essential to know what treatment the patient was taking. Access to the unblinding option will be granted only to the Investigators and sub-Investigators at the sites. If the treatment code has been opened, this must be recorded in the eCRF.

**The IWRS will immediately notify the Sponsor/CRO pharmacovigilance and the Clinical Trial Monitor whenever a treatment code is unblinded.**

Users from CRO and Sponsor Pharmacovigilance will have their own passwords to unblind patients in case of suspected unexpected serious adverse reactions (SUSARs) to be reported to the CA and ECs as applicable.

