### **8.2.2 Exclusion Criteria**

Patients are not eligible for the study if they meet one or more of the exclusion criteria listed below:

1. Any form of Parkinsonism other than IPD.
2. Diagnosis of chronic migraine (>15 days per month) or cancer pain.
3. L-dopa infusion.
4. Hoehn and Yahr stage 5 during the “ON” phase.
5. If female, pregnancy or breast-feeding.
6. Neurosurgical intervention of PD or stereotactic brain surgery.
7. Severe peak dose or biphasic dyskinesia, unpredictable or widely swinging fluctuations.
8. History of major depression or other clinically significant psychotic disorder which compromise the ability to provide the informed consent or to participate to the study.
9. Drug and/or alcohol abuse within 12 months prior to the screening visit.
10. History of dementia or severe cognitive dysfunction.
11. Use of any investigational drug or device within 30 days prior to screening or 5 half-lives, whichever is the longest, or during the study.
12. Allergy/sensitivity or contraindications to the investigational medicinal products (IMPs) or their excipients, to anticonvulsants or to anti-Parkinson drugs.
13. Any clinically significant condition (including laboratory values) which, in the opinion of the Investigator, would not be compatible with study participation or represent a risk for patients while in the study.
14. Moderate or severe liver failure using the Child-Pugh classification score, or human immunodeficiency virus (HIV) infection.
15. Treatment with monoamine oxidase inhibitors (MAOIs), pethidine, opiates, opioids, fluoxetine, fluvoxamine in the 4 weeks prior to the screening visit. These drugs are not allowed throughout the study and up 2 weeks after the last dose of study drug.
16. Ophthalmologic history including any of the following conditions: albinism, uveitis, retinitis pigmentosa, retinal degeneration, active retinopathy, severe progressive diabetic retinopathy, inherited retinopathy or family history of hereditary retinal disease.

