## 17.4 Definition of Serious Adverse Events or Serious Adverse Drug Reaction

A Serious Adverse Event (SAE) or Serious Adverse Reaction (SAR) is: “any untoward medical occurrence or effect that at any dose ”.

- Results in death.

- Is life-threatening (i.e. the patient was at risk of death at the time of the event/reaction; it does not refer to an event/reaction which hypothetically might have caused death if it were more severe).
- Requires inpatient hospitalisation or prolongation of existing hospitalisation.
- Results in persistent or significant disability/incapacity (where disability is defined as a permanent or substantial disruption of ability to carry out normal life functions, either reported or defined as per clinical judgement).
- Is a congenital anomaly/birth defect.
- Is an important medical event that may not result in death, be life-threatening, or require hospitalisation but, according to appropriate medical judgment, it may jeopardise the patient and may require medical or surgical intervention to prevent any of the outcomes listed in the definition above. Examples of such events include allergic bronchospasm requiring intensive treatment in an emergency room or at home, and blood dyscrasias or convulsions that do not result in hospitalisation, or development of drug dependency or drug abuse.

Any suspected transmission via a medicinal product of an infectious agent is also considered an SAE.

A non-serious adverse event (non-SAE) is any AE that does not meet the criteria listed above for an SAE.

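### Section 14.1 forbids the investigator to break the code except for a life-threatening SAE, then requires it in any emergency where the investigator thinks the treatment must be known

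*Protocol*

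**What the plan says.** Section 14.1 (Code Breaking) has three relevant statements.

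- **Opening sentence.** The investigator may not open the code for an individual patient while the trial runs, "except in the circumstance of an SAE of life-threatening significance". This is a prohibition with a single exception, defined by the type of event.
- **Second paragraph.** "In case of emergency, unblinding of the treatment code will be done through IWRS". This sets the route and does not tie the emergency to a life-threatening SAE.
- **Third paragraph.** "Unblinding of the study treatment must be done in case of an emergency situation, where the Investigator considers it essential" to know what the patient was taking. This is a duty, triggered by the investigator's judgement.

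The third paragraph also reserves the unblinding option to investigators and sub-investigators at the sites and requires any code break to be recorded in the eCRF.

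Three other sections bear on the point. Section 17.4 explains life-threatening to mean that "the patient was at risk of death at the time of the event/reaction", and excludes events that might have been fatal had they been worse. Section 18.3 makes the investigator responsible for breaking the code only as the protocol permits. Section 14.0 provides for an "emergency deviation from the CTP applicable only when an emergency situation has to be faced for a patient", applied to that patient alone, with a telephone call to the CRO as soon as possible.

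Both protocol versions in the file carry the same wording in Section 14.1.

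**The concern.** The two rules have different triggers. The opening sentence looks at the grade of the event; the third paragraph looks at whether the investigator needs to know the treatment. Where the triggers diverge, the investigator cannot comply with both, and Section 18.3 makes compliance a personal responsibility.

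What is at stake is patient safety. A site that reads the opening sentence as the rule could hesitate, or treat a necessary code break as an emergency deviation under Section 14.0.

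An illustration, which is not the protocol's: a patient with a fracture needs opioid analgesia. The emergency need not put the patient at risk of death. Exclusion criterion 15 (Section 8.2.2) covers opioids and pethidine and adds: "These drugs are not allowed throughout the study and up 2 weeks after the last dose of study drug". The restriction outlasts dosing, so stopping study drug does not tell the treating physician whether the patient had been exposed to safinamide.

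**Working it through.** No figure in the protocol depends on this point, so there is no arithmetic. The check is whether the two rules can be satisfied together in each situation that can arise.

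**Step 1. Can an emergency be serious without being life-threatening in the protocol's sense?** Yes. Section 17.4 lists several separate SAE criteria. Risk of death at the time of the event is one; need for inpatient admission is another. The protocol therefore recognises serious events that carry no immediate risk of death.

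**Step 2. Apply both rules to each case.**

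| Situation | Opening sentence | Third paragraph | Result |
|---|---|---|---|
| Life-threatening SAE, investigator considers the treatment essential to know | Permitted | Required | Consistent |
| Life-threatening SAE, treatment not considered essential to know | Permitted | Not required | Consistent |
| Other emergency, treatment considered essential to know | Forbidden | Required | **Conflict** |
| Other emergency, treatment not considered essential to know | Forbidden | Not required | Consistent |

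The conflict is confined to the third row, which is also where a clear rule matters most to the patient.

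**Step 3. Does any other text settle it?** Section 14.1 gives no order of precedence. Section 18.3 only refers back to the protocol. Section 14.0 allows a deviation for one patient in an emergency, which offers a way out. But that would make an act required by the third paragraph a deviation from the opening sentence of the same section, which leaves the contradiction in place.

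**Step 4. Is there an effect on the analysis?** No. Section 20.4.2 analyses FAS patients in the group to which they were randomised, so a code break does not move a patient between arms. The sample size and significance level do not depend on the code-break rule.

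**The case against.** The strongest reply is that Section 14.1 works in practice. The opening sentence states the general restriction, and the paragraphs directly beneath it are the operating instructions. The more protective text is the mandatory one, and a reader would have to stop after one sentence to be misled. Investigators and sub-investigators can unblind in the IWRS themselves. No sponsor approval step is stated, and the sponsor and CRO are notified after the event. Section 14.0 asks for a telephone call, not prior permission. This stands as far as the size of the harm goes: delay is possible, not certain, and nothing shows the IWRS refusing access. It does not remove the conflict, because having access to the system does not tell a site whether it is allowed to use it.

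Second, the opening sentence speaks of life-threatening significance and does not cross-refer to Section 17.4, so the strict definition may not apply. That is fair, but a looser reading only narrows the gap. The exception would still depend on the grade of an SAE and not on the need to know the treatment. If, conversely, emergency in the third paragraph were read to mean only a life-threatening SAE, the rules would agree, but at the price of barring unblinding in every other emergency, however essential. The opening sentence needs changing on either reading.

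Third, the opioid illustration has limits. Criterion 15 does not distinguish between arms, so learning that a patient took placebo would not lift the bar on paper. Section 15 also lists intercurrent illness needing a non-permitted drug as a reason for withdrawal. Both points are correct. Withdrawal does not reveal the treatment, though, and knowing it could still affect clinical care. Equally, no text says that a code break under the third paragraph must be logged as a deviation; Section 14.1 asks only for an eCRF entry. The finding does not rest on either argument.

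**Conclusion.** The concern holds as a minor inconsistency within one section. For an emergency that is not life-threatening but in which the investigator considers the treatment essential to know, Section 14.1 both forbids and requires unblinding, and nothing in the protocol says which rule governs.

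The consequence is possible delay in unblinding. That is inferred from the wording and is not stated in the protocol. Few of the 306 planned patients are likely to be affected; this is a judgement, since the protocol gives no expected number of code breaks. There is no effect on type I error, power or the FAS analysis.

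**What to change.** Replace the opening sentence of Section 14.1 with one that carries the third paragraph's criterion, for example: *The Investigator may break an individual patient's code only in a medical emergency in which, in the Investigator's judgement, knowing the treatment is essential to managing that patient.*

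This removes the restriction to life-threatening SAEs and leaves one threshold. It does not open the way to routine unblinding. The IWRS notification, the eCRF record and the pharmacovigilance route for SUSARs stay as they are. Section 18.3 needs no edit because it only points to the protocol.

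The cost is one sentence of protocol wording, with no statistical cost. The only downside is possibly a few more code breaks.
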